#### 3.1 PARTICIPANT INCLUSION CRITERIA

1. Born to male gender, age 18 years or more
2. Previously attended the enrolling clinic on at least one occasion
3. Completed a screen for HIV and STIs
4. HIV negative by a routinely used assay within 4 weeks prior to or on the day of randomisation
5. Reported unprotected anal intercourse (UAI) on more than one occasion within the 90 days prior to randomisation
6. Likely, in the opinion of the volunteer, to have UAI in the next 90 days
7. Willing and able to comply with the visit schedule throughout the follow-up period
8. Willing and able to provide written informed consent

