#### 5.2.2 DISPENSING

The Principal Investigator will ensure that Truvada is dispensed in accordance with the protocol and local procedures as appropriate. Local Working Instructions will be reviewed at site initiation. Truvada will be stored in a secure, limited access storage area under the specified storage requirements.

The Principal Investigator will ensure that records are maintained showing the receipt, dispensing and destruction of all Truvada. A drug accountability log will be kept to record the identification of the participant to whom the Truvada was given and the date they received drug. The aim will be to provide sufficient to last beyond the next scheduled visit. Any unused Truvada that is returned will also be documented.

It may be necessary for a member of the clinic study team to dispense Truvada at times when a pharmacist is not present. Where this is the case the Principal Investigator will ensure a robust system is in place to capture all required dispensing information.

It may be necessary for drug to be posted to ensure continued supply. When this is the case the Principal Investigator will ensure a robust system is in place to capture the result of the HIV test and urinalysis.

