#### **6.2.1.C Post-randomisation procedures**

All participants will receive support to adhere to the agreed plan to manage their personal risk, and counselling about the importance of adhering to the agreed schedule of visits. All participants will be provided with sufficient monthly questionnaires to last until the next visit, and stamped addressed envelopes if they have selected to complete these manually. A diary will also be provided to record acts of anal intercourse and condom use, different partners, and pill taking when applicable.

A blood sample to confirm HIV status using an antigen/antibody assay should be collected and processed according to the clinic routine. In the event of an indeterminate or positive result, the participant will be recalled for further investigation.

For participants starting Truvada IMMEDIATELY, at month 12 or earlier, the clinician and participant will go through the instructions for use of with Truvada (see [Sections 5.2.1 Treatment Schedule](#)). They will be issued with 1 bottle, containing 30 tablets, and the next clinic appointment will be made before they could run out of drug. They will be asked to tick the days they take drug on the diary. The clinician will ensure that the participant understands that

- it takes two weeks before drug has reached a steady level in the tissues and that the drug may be less effective during this period
- their risk may not be reduced if they have missed 3 or more tablets in the week before unprotected anal intercourse
- starting or restarting Truvada when they have caught HIV increases the chance of resistance to Truvada

The clinician will use this information to advise participants on the circumstances in which they should consider post-exposure prophylaxis.

A blood sample will be collected to determine renal function, using serum creatinine to estimate the glomerular filtration rate.

Following a recommendation from the Trial Steering Committee on 9th October 2014, participants who are still in the first 12 months of the deferred period are to be recalled and offered Truvada. They will be provided with a supplementary PIS - New Information about treatment being studied (Appendix X) and asked to sign the accompanying consent (Appendix XI), after which the clinician and participant will go through the instructions as described in Sections 5.2.1 Treatment Schedule and 6.2.1.C Post-randomisation procedures above.

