### 6.2.3 QUARTERLY CLINIC FOLLOW-UP (MONTHS 3, 6, 9, 12, 15, 18, 21, 24, AND 3 MONTHLY TO EXIT)

Three monthly checks of HIV status and an STI screen are required for **all participants**. These visits may be conducted on the telephone supported by data collected in another clinic.

There will be contact with the study team to review the participant's personal risk reduction plan and determine whether additional support is required. A short questionnaire will be completed during the study clinic visit, or at the time of drug collection if the contact takes place on the telephone or via NHS email, and placed in a sealed envelope to be sent to MRC CTU.

During periods in which the participant is taking Truvada, the clinician will ascertain whether there have been any side-effects sufficient to lead to interruption of drug, and any serious adverse events.

During this visit the following investigations will be performed according to clinic routine:

- HIV test
- Urethral, rectal and pharyngeal swabs for *Chlamydia trachomatis* and *Neisseria gonorrhoea*
- serology for syphilis and hepatitis C when indicated
- Urinalysis

If these tests have been collected since the previous study visit, either at the enrolling clinic or another clinic, the results already available will be used, and tests only collected on the day of the visit if clinically indicated.

In the presence of 1 + of protein in the urine of a participant who is taking Truvada, and the absence of nitrites which makes a urinary tract infection less likely, a blood or urine sample will be collected to check renal function according to clinic routine.

A blood specimen may be collected for the analysis of drug levels.

Unused pills will be recorded on the case record form, and checked directly if the participant brought these to clinic. Sufficient drug will be dispensed to last beyond the next appointment approximately

three months later. Up to six months can be dispensed provided the participant is able to obtain a HIV test through another clinic or self-sampling and communicate the result to the study team.

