#### 6.2.4 ANNUAL CLINIC FOLLOW-UP AND EXIT

These visits are required for **all participants**.

Annual and Final visits will be performed as Quarterly Visits.

In addition participants will be asked to complete a long behaviour and lifestyle questionnaire in private in the clinic, and place this in a sealed envelope to be sent to MRC CTU. The following will also be performed:

- Urine/urethral swab and rectal swab for *Chlamydia trachomatis* and *Neisseria gonorrhoea*
- serology for syphilis and hepatitis C when indicated, except at the final visit when a sample will be collected regardless of risk
- serum for creatinine

If these tests have been collected proximal to the due date according to the schedule, either at the enrolling clinic or another clinic, the results already available will be used, and tests only collected on the day of the visit if clinically indicated.

A blood sample to confirm HIV status using an antigen/antibody assay should be collected and processed, regardless of whether or not this is indicated according to the clinic routine.

If the participant is willing, an acceptability questionnaire will be completed during the clinic visit, and placed in a sealed envelope to be sent to MRC CTU.

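### The substitution sentence in section 6.2.3 secures one HIV test per between-visit interval rather than the three-monthly check the section requires, so gaps of just under 6 months are possible with Truvada resupplied in between

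*Protocol*

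**What the plan says.** **Required frequency.** Section 6.2.3 opens: "Three monthly checks of HIV status and an STI screen are required for" all participants. The visits are at months 3, 6, 9, 12 and so on. The Trial Assessment Schedule marks the HIV test and urinalysis for protein as mandatory in the quarterly column.

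**Substitution.** After listing the HIV test, swabs, serology and urinalysis, the same section continues: "If these tests have been collected since the previous study visit, either at the enrolling clinic or another clinic". In that case the available results are used, and visit-day tests are taken only on clinical indication. The previous study visit is the only limit on the age of the result.

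**Annual and exit visits.** Section 6.2.4 has a parallel sentence with a different condition: "If these tests have been collected proximal to the due date according to the schedule". It follows a list of swabs, syphilis and hepatitis C serology, and creatinine. HIV is handled separately there: a confirmatory blood sample is to be taken whether or not clinic routine calls for one.

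**Supply.** Standard dispensing lasts to just beyond the next appointment, about three months away. In addition: "Up to six months can be dispensed provided the participant is able to obtain a HIV test through another clinic or self-sampling", with the result passed to the study team. No timing is given for that test. Where drug is posted, section 5.2.2 says "the Principal Investigator will ensure a robust system is in place to capture the result of the HIV test and urinalysis".

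**Resistance.** Participants are told that "starting or restarting Truvada when they have caught HIV increases the chance of resistance to Truvada" (section 6.2.1.C). Section 8.1 describes a small risk of resistance from continuing Truvada after seroconversion. Section 9.2.2 lists K65R and M184V mutations among the outcomes.

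**The concern.** The substitution sentence and the opening sentence of section 6.2.3 set different standards. One asks for a check every three months. The other asks for a result from somewhere in the interval since the last visit. A result from the start of one interval followed by a result from the end of the next satisfies the second standard but not the first.

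Two things depend on the spacing. The quarterly test is how HIV infection, a listed outcome, is detected between annual visits. It is also what limits how long an infected but undiagnosed man goes on receiving Truvada, and so it affects the resistance outcome.

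A related mismatch concerns supply. Six-month dispensing names an HIV test only. Posting names an HIV test and urinalysis. The schedule makes quarterly urinalysis mandatory for everyone. Sites therefore have three statements to work from on which results accompany supply of the same drug.

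**Working it through.** **Inputs** (sections 6.2.3 and 6.2.4)
- Quarterly visits at months 3, 6, 9, 12, 15, 18, 21, 24.
- A substituted result may date from any time after the previous study visit. I take one day after as the extreme: 1/30.4 = 0.03 month.
- The HIV sample is fixed at months 12 and 24.
- Supply is about 3 months as standard and up to 6 months when extended.

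Gap = date of next HIV test − date of last HIV test.

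**1. The plan's own figure.** If every test is done on the visit day, the largest gap is 6 − 3 = 3 months. The required interval is reproduced.

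**2. Substitution, every visit held.**
- A test one day after the month 15 visit is at 15.03. It serves month 18, where it is 18 − 15.03 = 2.97 months old, and drug is dispensed.
- The next test is on the day of the month 21 visit.
- Gap = 21 − 15.03 = 5.97 months.
- Enumerating all patterns over months 0 to 24, with each quarterly test either one day after the previous visit or on the visit day, gives the same maximum of 5.97 months.
- A less extreme case is a test about a week after month 3 (taken as 3.25), used at month 6 and followed by a test at month 9: 9 − 3.25 = 5.75 months. The month 6 resupply then rests on a result 2.75 months old, about 12 weeks.

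**3. One quarterly contact missed.**
- Six months of drug is dispensed at month 3. An outside test at month 3.25 is reported to the team. This meets the supply condition, which sets no timing.
- Month 6 is missed. At month 9 the previous study visit is still month 3, so the same result qualifies, now 9 − 3.25 = 5.75 months old.
- The annual sample fixes the next test at month 12. Gap = 12 − 3.25 = 8.75 months.
- With the test one day after month 3, the gap is 12 − 3.03 = 8.97 months.

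**4. Results named alongside supply**

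| Where | HIV test | Urinalysis |
|---|---|---|
| Schedule, quarterly visit | mandatory | mandatory |
| 6.2.3, six-month supply | named, no timing | not named |
| 5.2.2, posted drug | named | named |

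**5. Delay to detection.** Assume, for illustration, that infection is equally likely at any point in a gap and that the next test detects it. The mean delay is half the gap: 3/2 = 1.5 months as intended, 5.97/2 = 2.98 months in case 2, and 8.97/2 = 4.48 months at the extreme of case 3. For a man with uninterrupted supply, the delay is also the time on Truvada while infected and undiagnosed.

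**The case against.** The strongest reply is that this is a deliberate and reasoned choice. The version 1.3 amendment note (section 16) explains that evening and weekend clinics proved easier for participants, and that staff can see those results before prescribing. That fits the pragmatic aim in section 1.3. One test per interval is still obtained, so the fault is spacing and not omitted tests. A clinically indicated test remains possible, and section 8.1 provides a cross-check against the national database of new HIV diagnoses. All of this stands. It supports using outside results, but it does not explain why the date within the interval is left open when the section itself asks for three-monthly checks.

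Several stronger readings are tempting and are not supported:
- *Results of any age are accepted.* They must postdate the previous study visit, so on schedule they are at most about 3 months old.
- *Gaps of 6 to 9 months are what the rule ordinarily allows.* With visits held, the ceiling is just under 6 months. Anything longer needs a missed contact, which itself departs from the section.
- *The four-week limit at entry (section 3.1) shows the follow-up rule is too loose.* That is an eligibility criterion with a different purpose.
- *Section 6.2.4 sets a recency rule for HIV tests.* Its list does not name HIV, and no window is stated. It is useful only as an example of wording tied to the due date.
- *Infections will be dated from the wrong visit.* Nothing in the protocol dates endpoints by visit, and section 9.5 censors incomplete follow-up at the last negative test.
- *Six-month supply waives urinalysis.* The sentence adds an HIV condition and is silent on urinalysis. It does not cancel the requirement in the schedule.

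**Conclusion.** The point holds in a limited form. As written, section 6.2.3 does not secure its own three-monthly HIV check. The largest gap is just under 6 months with every visit held, about twice the intended interval, with Truvada resupplied in between. It can approach 9 months if one quarterly contact is missed.

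These are the extremes the text allows, not estimates of what happened. They assume early outside tests, no clinically indicated visit-day test and, for the longer figure, no further test before the next fixed annual sample. The documents do not show how many of the 545 enrolled men have such a pattern.

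The effect is later detection of infection and possibly longer Truvada exposure after it, which matters most for the resistance outcome. On that risk, section 8.1 is the relevant statement, and it calls the risk small; the warning in 6.2.1.C concerns starting or restarting. The annual sample anchors month 12, so the effect there is limited. The main outcomes, accrual and retention, are untouched.

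The supply mismatch is a separate, smaller point: three statements name different results, and they need to agree.

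**What to change.** - Reconcile the substitution sentence of 6.2.3 with that section's three-monthly requirement and with the schedule. One way is to tie a substituted result to the due date of the visit it serves, as 6.2.4 already does for its listed tests.
- Reconcile the six-month supply sentence in 6.2.3 and the posting condition in 5.2.2 with each other and with the quarterly urinalysis in the schedule, and state the timing intended for the outside HIV test. Which clinical condition applies is for the sponsor to decide.

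The cost is a short amendment (one sentence for the substitution rule, plus aligned wording on supply) and an update to the working instructions. The downside is that a few participants with an early outside result would need one further routine test. The convenience of using results from other clinics is kept.

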#### 6.2.4 ANNUAL CLINIC FOLLOW-UP AND EXIT

These visits are required for **all participants**.

Annual and Final visits will be performed as Quarterly Visits.

In addition participants will be asked to complete a long behaviour and lifestyle questionnaire in private in the clinic, and place this in a sealed envelope to be sent to MRC CTU. The following will also be performed:

- Urine/urethral swab and rectal swab for *Chlamydia trachomatis* and *Neisseria gonorrhoea*
- serology for syphilis and hepatitis C when indicated, except at the final visit when a sample will be collected regardless of risk
- serum for creatinine

If these tests have been collected proximal to the due date according to the schedule, either at the enrolling clinic or another clinic, the results already available will be used, and tests only collected on the day of the visit if clinically indicated.

A blood sample to confirm HIV status using an antigen/antibody assay should be collected and processed, regardless of whether or not this is indicated according to the clinic routine.

If the participant is willing, an acceptability questionnaire will be completed during the clinic visit, and placed in a sealed envelope to be sent to MRC CTU.

#### **For participants already on Truvada PrEP**

At their next appointment all participants will be provided with a supplementary PIS - New Information about treatment being studied (Appendix X) and asked to sign a consent (Appendix XI) .

### 6.3 PROCEDURES FOR ASSESSING HIV SEROCONVERSION

Presumptive HIV infections should be confirmed according to criteria developed by UK Standards for Microbiology Investigations. A repeat sample should be obtained and reactivity confirmed by a sensitive HIV RNA assay.

### 6.4 PROCEDURES FOR ASSESSING SAFETY

Participants will be asked one month after starting Truvada and quarterly whether they have had any admissions to hospital, or suffered any significant illnesses that stopped them undertaking their usual daily activities and required medical intervention. A clinical member of the team will determine whether or not an illness that interfered with usual daily activity meets the definitions for Serious Adverse Event (SAE) provided in [Table 7.1: Definitions](#). SAEs should be reported to MRC CTU within 24 hours of the investigator becoming aware of this. Participants will also be asked whether they have had any side-effects sufficient to interrupt or stop their Truvada.

Glomerular filtration rate will be estimated at baseline, and annually. Urinalysis for protein will be assessed at these and interim visits and the presence of 1+ or greater protein that cannot otherwise explained will trigger an additional investigation according to routine clinic practice for patients taking Truvada (either a further creatinine measurement to estimate glomerular filtration rate, or urinary protein:creatinine ratio). In the event that that estimated glomerular filtration rate (eGFR) is less than 50mL/min, or the ratio of protein: creatinine (UPC) greater than 20, the participant will be recalled, their medical history, other medication, dietary supplements and pill taking reviewed, and a repeat test performed in the absence of any protein supplements. If the eGFR is confirmed to be < 50 mL/min or the UPC > 20, then Truvada may need to be interrupted or modified to 4 or less tablets a week pending further investigation and/or referral for specialist opinion. In the event that this leads to discontinuation of Truvada, this meets the definition of 'another important medical condition' as described in [Table 7.1: Definitions](#), and should be reported to MRC CTU within 24 hours of the investigator becoming aware of the event.

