## SUMMARY OF TRIAL

SUMMARY INFORMATION TYPE	SUMMARY DETAILS
ACRONYM	PROUD
Long Title of Trial	Pre-exposure Option for reducing HIV in the UK: an open-label randomisation to immediate or deferred daily Truvada for HIV negative gay men.
Version	1.3
Date	14 October 2014
ISRCTN #	ISRCTN94465371
NCT#	NCT02065986
EudraCT #	2012-002373-56
Study Design	A multi-centre, open label randomised design to immediate or deferred inclusion of pre-exposure prophylaxis as part of the package of HIV risk reduction interventions.
Type of Participants to be Studied	HIV negative men who have unprotected anal intercourse (UAI) with men
Setting	Genito-urinary medicine (GUM) clinics in the UK
Interventions to be Compared	All participants will be offered a risk reduction package that includes regular HIV testing, diagnosis and treatment of sexually transmitted infections (STI), support to reduce and eliminate high risk behaviour including free condoms, and other biomedical interventions such as post-exposure prophylaxis where relevant. With or Without the inclusion of daily oral Truvada.
Study Question	In order to determine whether the immediate inclusion of anti-retroviral pre-exposure prophylaxis (PrEP) as part of the HIV risk reduction package for men who have sex with men who are at risk of acquiring HIV is clinically effective and cost-effective, a large trial would need to be conducted.  The purpose of the pilot is to determine the feasibility of conducting such a trial in the UK.
Main Outcome Measures	Time to accrual of 500 participants Retention at month 12 and 24
Other Outcome Measures	HIV infection between randomisation and month 12 .  Safety: 
 
• Serious Adverse Reactions attributable to Truvada
 
• Adverse events that lead to interruption or cessation of Truvada
 
• Renal function estimated using serum creatinine at 12m
 
• Frequency of viral resistance in men who acquire HIV
 

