#### **6.2.2 FOLLOW-UP AFTER ONE MONTH ON TRUVADA:**

This assessment, which can take place in the clinic or by telephone, is required for

- **participants randomised to IMMEDIATE Truvada** at month 1
- **participants randomised to DEFERRED Truvada** at month 13 (or earlier)

There will be an interview to see if the participant has experienced any side-effects sufficient to interrupt Truvada, and how they are managing to fit the daily pill into their routine schedule. Urine will be collected for analysis if they attend a study clinic. In the presence of 1 + of protein in the urine of a participant who is taking Truvada, and the absence of nitrites which makes a urinary tract infection less likely, a blood or urine sample will be collected to check renal function according to clinic routine.

A short questionnaire will be completed either during the study clinic visit or at the time of drug collection if the visit is conducted on the telephone, and placed in a sealed envelope to be sent to MRC CTU. If participants prefer to enter their data directly into the participant database they may do so.

A blood specimen may be collected for the analysis of drug levels.

Unused pills will be recorded on the case record form, and checked directly if the participant brought these to clinic. Sufficient drug will be dispensed to last beyond the next appointment approximately two months later. If the study assessment was conducted on the telephone, the participant will need to attend to collect their drugs.

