**TABLE 7.1: DEFINITIONS**

TABLE	DEFINITION
Adverse Event (AE)	Any untoward medical occurrence in a participant or clinical trial subject to whom a medicinal product has been administered including occurrences that are not necessarily caused by or related to that product.
Adverse Reaction (AR)	Any untoward and unintended response to an investigational medicinal product related to any dose administered.
Unexpected Adverse Reaction (UAR)	An adverse reaction, the nature or severity of which is not consistent with the information about the medicinal product in question set out in the Summary of Product Characteristics (SPC) or Investigator Brochure (IB) for that product.
Serious Adverse Event (SAE) or Serious Adverse Reaction (SAR) or Suspected Unexpected Serious Adverse Reaction (SUSAR)	Respectively any adverse event, adverse reaction or unexpected adverse reaction that: 
 
▪ Results in death
 
▪ Is life-threatening*
 
▪ Requires hospitalisation or prolongation of existing hospitalisation**
 
▪ Results in persistent or significant disability or incapacity
 
▪ Consists of a congenital anomaly or birth defect
 
▪ Is another important medical condition***
 

\*The term life-threatening in the definition of a serious event refers to an event in which the participant is at risk of death at the time of the event; it does not refer to an event that hypothetically might cause death if it were more severe, for example, a silent myocardial infarction.

\*\*Hospitalisation is defined as an inpatient admission, regardless of length of stay, even if the hospitalisation is a precautionary measure for continued observation. Hospitalisations for a pre-existing condition (including elective procedures that have not worsened) do not constitute an SAE.

\*\*\* Medical judgement should be exercised in deciding whether an AE or AR is serious in other situations. The following should also be considered serious: important AEs or ARs that are not immediately life-threatening or do not result in death or hospitalisation but may jeopardise the subject or may require intervention to prevent one of the other outcomes listed in the definition above; for example, a medical event that leads to the permanent discontinuation of Truvada; an allergic bronchospasm requiring intensive emergency treatment, seizures or blood dyscrasias that do not result in hospitalisation or development of drug dependency.

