### 7.1.2 EXEMPTED ADVERSE EVENTS

Adverse Events include:

- Any event that leads to the interruption or discontinuation of Truvada, regardless of relationship
- Any event the Investigator considers important to the safety evaluation of Truvada, including bone fractures, renal events and unexplained abdominal pain or headaches
- Overdose of Truvada without signs or symptoms

and any Serious Adverse Event that is:

- An exacerbation of a pre-existing illness
- An increase in frequency or intensity of a pre-existing episodic event or condition
- A condition detected after trial drug administration (even though it may have been present prior to enrolment)
- Continuous persistent disease or a symptom present at baseline that worsens following administration of the study treatment

Adverse Events do not include:

- Medical or surgical procedures; the condition that leads to the procedure is the adverse event
- Pre-existing disease or a condition present before treatment that does not worsen
- Hospitalisations where no untoward or unintended response has occurred, eg, elective cosmetic surgery, social admissions

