#### 9.2.2 OTHER OUTCOME MEASURES

- HIV infections acquired between trial entry and 12 months, and between 12 and 24 months
- Safety
  - Serious Adverse Reactions attributable to Truvada
  - Any adverse event leading to interruption or discontinuation of Truvada
  - Renal function estimated using serum creatinine at 12 months
  - Presence of viral resistance mutations likely to have been selected by Truvada (K65R, M184V) in participants who acquire HIV infection.
- Adherence:
  - Proportion of doses taken estimated from self-report
  - Proportion of days covered according to dispensing records for the daily schedule
  - Presence of drug as expected in a subset of selected participants
- Risk Compensation:
  - Number of sexual partners with whom had UAI, UIAI and URAI (unprotected defined as without a condom) between trial entry and month 12 and month 12 to month 24
  - Number of acts of AI, protected and unprotected by a condom, between trial entry and month 12 and month 12 to 24
  - Proportion of acts of AI protected by either condom, PrEP or both between trial entry and month 12 and month 12 to 24
  - Sexually transmitted infection (STIs) acquired between trial entry and month 12
  - Sexually transmitted infection (STIs) acquired between month 12 and month 24
- Other:
  - Facilitators and barriers to adherence to a personal risk reduction plan in a subset of selected participants

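### Truvada interruptions are asked about only as side-effects, while the safety outcome counts any adverse event that leads to one, so temporary stops for minor illness not blamed on the drug may be missed

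*Protocol*

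**What the plan says.** **The outcome.** The Summary of Trial lists "Adverse events that lead to interruption or cessation of Truvada" and Section 9.2.2 lists "Any adverse event leading to interruption or discontinuation of Truvada". Neither sets a condition on causality. Table 7.1 defines an adverse event as "including occurrences that are not necessarily caused by or related to that product". Section 7.1.2 brings into scope "Any event that leads to the interruption or discontinuation of Truvada, regardless of relationship".

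**How it is collected.** Three sections tell sites what to ask about interruptions:

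- Section 6.2.2, one month after starting: "There will be an interview to see if the participant has experienced any side-effects sufficient to interrupt Truvada".
- Section 6.2.3, quarterly while on drug: "the clinician will ascertain whether there have been any side-effects sufficient to lead to interruption of drug, and any serious adverse events".
- Section 6.4, general safety procedures: "Participants will also be asked whether they have had any side-effects sufficient to interrupt or stop their Truvada".

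Section 6.4 also has participants asked, with no reference to cause, about hospital admissions and about illnesses that both kept them from normal activity and needed medical attention. Its stated use is to decide whether an event is a serious adverse event (SAE).

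**The concern.** An adverse event, as Table 7.1 defines it, need not be caused by the drug. A side-effect is by ordinary meaning an effect of the drug, which is closer to the table's adverse reaction. All three interruption questions use the narrower term, so this is not a single slip of the pen. A man who left off his tablets for a week because of a minor illness that he put down to something else could truthfully report no side-effect, yet his event belongs in the Section 9.2.2 outcome.

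At stake is how complete one secondary safety count is. The protocol's outcome leaves attribution out, but the wording of the question puts part of it back before the investigator has assessed anything. An analysis plan cannot repair this later, because events never elicited are not in the data.

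**Working it through.** No arithmetic applies. The protocol states no expected rate for this outcome, and Section 9.3 describes the pilot's size as a pragmatic choice. The check is to take each kind of event that could lie behind a stop and ask which procedure would find it.

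| Event behind the stop | Procedure that would find it | Depends on blaming the drug? |
|---|---|---|
| Hospital admission or other SAE | 6.2.3, 6.4 and the SAE determination at every contact in 7.3.1.A | No |
| Medical event ending Truvada permanently | Given in the notes to Table 7.1 as an example of a serious event, so within the same SAE determination | No |
| Significant illness that stopped usual activity and needed medical care | Illness question in 6.4 | No |
| Renal abnormality | Urine protein and creatinine monitoring in 6.4 and 7.1.3; renal function is also a 9.2.2 outcome | No |
| Non-serious event that the participant attributes to Truvada | Side-effects question in 6.2.2, 6.2.3 and 6.4 | Yes, and it is found |
| Temporary stop for a non-serious illness, injury or symptom below the 6.4 threshold, not attributed to Truvada | No direct question | Yes, and it may be missed |

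The last row meets the outcome definition in Sections 9.2.2 and 7.1.2. Two indirect routes might still bring it to light:

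1. **Pill accountability.** Unused tablets are recorded at the contacts in 6.2.2 and 6.2.3, and Section 5.4 has the clinic look for an explanation of an excess or shortfall. No text sends that explanation to adverse event recording. Tablets are checked directly only if the participant brings them, quarterly contacts may be by telephone, and up to six months' supply may be dispensed (6.2.3).
2. **The diary.** Section 6.5.1 has it record whether a pill was taken, not why one was missed. Section 16 (version 1.3) reports poor completion.

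These routes may recover some such events, but they do not replace a direct question.

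**The case against.** The strongest reply is that the protocol looks for most important events regardless of cause, and it largely stands. A reader might infer from the interruption wording that visits ask about nothing but side-effects. The table above shows otherwise. A reader might also infer that the events named in Section 7.1.2 go unsought. For renal events this is wrong, because they are found by measurement. A fracture treated as an outpatient needs medical care and may well meet the illness question in 6.4.

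Nor does it follow that those named events should become outcomes or be prompted for one by one. Section 7.1.2 describes "Any event the Investigator considers important to the safety evaluation of Truvada, including bone fractures, renal events and unexplained abdominal pain or headaches", which leaves the choice to the investigator. The protocol nowhere promises to elicit them systematically, so there is no contradiction to resolve.

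It can also be said that in 6.2.3 it is the clinician who ascertains, and that the wording actually used sits in the visit case record form, which is not shown. Both are fair. But what the clinician is told to ascertain is still side-effects. If the form already asks a neutral question, the protocol text should be brought into line with it.

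Finally, a reader might want a size, and might turn to the 7 of 4,500 in Section 1.2.1 who stopped Truvada for toxicity in earlier trials. That figure counts stops attributed to the drug. The events at issue here are those not attributed to it, so it is no benchmark.

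**Conclusion.** The mismatch is real: the protocol defines an outcome that ignores relationship and collects part of it with a question that presumes relationship. Its reach is narrow. It concerns mainly temporary interruptions for non-serious illness, injury or symptoms that the participant does not blame on Truvada.

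The documents support a risk that these are missed. They do not show that the outcome is undercounted, and they contain nothing from which to estimate how many events are lost, so no figure should be attached. The conclusion assumes that sites follow the protocol wording and that the unseen form is no broader.

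Severity is minor: one secondary safety outcome in a feasibility pilot, with serious and renal events covered elsewhere. It remains worth correcting although enrolment has closed. Version 1.3 offers Truvada early to deferred participants still in their first year (Sections 1.4 and 6.2.1.C), and quarterly contacts continue to exit, so further time on drug would be recorded under this wording.

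**What to change.** In Sections 6.2.2, 6.2.3 and 6.4, replace the side-effects question with one that asks whether, since the last contact, Truvada was interrupted or stopped for any illness, injury or symptom, whatever the participant believes the cause to be. Record the reason given, and have the investigator assess relationship afterwards. Align the case record form if it does not already read this way. Section 9.2.2 needs no change, and no treatment rule is affected.

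The cost is rewording in three places and a few more minor events to record. Counts before and after the change will not be directly comparable, because the later question is wider. Reporting the events judged drug-related separately, alongside the total, keeps a series that is closer to comparable across the change.
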